11.4.1.4 Secondary Efficacy Endpoints

11.4.1.4.1 Secondary Efficacy Endpoints Measured at Ventilatory Anaerobic Threshold

The 2 secondary efficacy endpoints measured at VAT indicated greater exercise capacity in the udenafil group than the placebo group at Week 26:

- VE/VCO₂ at VAT: Greater mean decrease (improvement) for udenafil (-0.76) as compared to placebo (-0.05) at Week 26 (p=0.011)
- Work rate at VAT: Greater mean increase (improvement) for udenafil (3.46 watts) as compared to placebo (0.31 watts) at Week 26 (p=0.029)

Change in secondary exercise endpoints measured at VAT from baseline to Week 26 are summarized in [Table 17](#).

Table 17: Difference in Secondary Exercise Endpoints Measured at Ventilatory Anaerobic Threshold Between Week 26 and Baseline Visits Using Last Observation Carried Forward (ITT Population)

Exercise Endpoint	Udenafil (N=200)	Placebo (N=200)	Difference LS Mean (SE)	p-value
VE/VCO₂ at VAT				
Baseline	n=170	n=181		
Mean (SD)	34.32 (4.845)	34.75 (5.157)	-0.42 (0.536)	0.431 ^a
Week 26	n=185	n=191		
Mean (SD)	33.60 (4.833)	34.67 (4.872)	-1.13 (0.509)	0.027 ^a
Difference, Week 26 – baseline	n=170	n=181		
Mean (SD)	-0.76 (3.564)	-0.05 (2.967)	-0.82 (0.321)	0.011 ^b
Median	0.00	0.00		
Work rate at VAT (watts)				
Baseline	n=167	n=177		
Mean (SD)	66.19 (26.321)	66.10 (23.446)	0.12 (2.688)	0.963 ^a
Week 26	n=181	n=186		
Mean (SD)	69.20 (26.171)	66.62 (22.710)	3.30 (2.660)	0.215 ^a
Difference, Week 26 – baseline	n=167	n=177		
Mean (SD)	3.46 (15.076)	0.31 (13.246)	3.20 (1.460)	0.029 ^b
Median	1.00	0.00		

ANCOVA=analysis of covariance; ANOVA=analysis of variance; ITT=intent-to-treat; LS=least squares; SD=standard deviation; SE=standard error; VAT=ventilatory anaerobic threshold; VE/VCO₂=ventilatory equivalents of carbon dioxide; VO₂=minute oxygen consumption

a P-value was assessed using ANOVA with fixed factors for ventricular morphology (single left versus single right or mixed) and treatment group.

b P-value was assessed using ANCOVA with fixed factors for ventricular morphology (single left versus single right or mixed) and treatment group with a continuous covariate of baseline maximal VO₂.

Source: [Table 14.2.13.1.1](#) and [Table 14.2.14.1.1](#)

Program: [T_14_2_13_1_1.sas](#) and [T_14_2_14_1_1.sas](#)

Results for treatment group differences in change from baseline for VE/VCO₂ at VAT were generally similar for analyses using no imputation (p=0.014, [Table 14.2.13.1.2](#)) and imputation with the mean of non-missing values at Week 26 (p=0.044, [Table 14.2.13.1.3](#)). Results for treatment group differences in percent change from baseline for VE/VCO₂ at VAT were generally similar for analyses using LOCF (p=0.008, [Table 14.2.13.2.1](#)), no imputation (p=0.010, [Table 14.2.13.2.2](#)), and imputation with the mean of non-missing values at Week 26 (p=0.035, [Table 14.2.13.2.3](#)).

Results for treatment group differences in change from baseline for work rate at VAT were generally similar for analyses using no imputation (p=0.021, [Table 14.2.14.1.2](#)) and imputation with the mean of non-missing values at Week 26 (p=0.011, [Table 14.2.14.1.3](#)). Results for treatment group differences in percent change from baseline for work rate at VAT

were generally similar for analyses using LOCF ($p=0.053$, [Table 14.2.14.2.1](#)), no imputation ($p=0.035$, [Table 14.2.14.2.2](#)), and imputation with the mean of non-missing values at Week 26 ($p=0.030$, [Table 14.2.14.2.3](#)).

11.4.1.4.2 Secondary Efficacy Endpoints Measured at Peak Exercise

The treatment group difference for change from baseline to Week 26 in VE/VCO₂ at peak exercise was statistically significant ($p=0.005$). A mean decrease of -1.24 was observed in the udenafil group as compared to a mean increase of 0.04 in the placebo group. For other efficacy endpoints measured at peak exercise (minute VO₂, respiratory rate, minute ventilation, work rate, heart rate, and RER), treatment group differences for change from baseline to Week 26 did not achieve $p\leq 0.05$. The change in secondary efficacy endpoints measured at peak exercise from baseline to Week 26 is summarized in [Table 18](#).

Table 18: Change in Secondary Efficacy Endpoints Measured at Peak Exercise Between Week 26 and Baseline Visits Using Last Observation Carried Forward (ITT Population)

Exercise Endpoint	Udenafil (N=200)	Placebo (N=200)	Difference LS Mean (SE)	p-value^a
Minute VO ₂ (L/minute)	n=200	n=200		
Difference, Week 26 – baseline, mean (SD)	0.04 (0.238)	0.00 (0.222)	0.04 (0.023)	0.071
Respiratory rate (breaths/minute)	n=199	n=200		
Difference, Week 26 – baseline, mean (SD)	-1.01 (10.030)	-1.44 (9.928)	0.35 (0.903)	0.696
Minute ventilation (L/minute)	n=199	n=200		
Difference, Week 26 – baseline, mean (SD)	1.15 (13.934)	-0.10 (13.748)	0.14 (1.319)	0.915
Work rate (watts)	n=198	n=199		
Difference, Week 26 – baseline, mean (SD)	2.99 (14.334)	2.45 (13.503)	0.19 (1.363)	0.891
Heart rate (beats/minute)	n=200	n=200		
Difference, Week 26 – baseline, mean (SD)	-1.36 (10.773)	-2.41 (12.714)	0.66 (1.140)	0.563
Respiratory exchange ratio	n=200	n=200		
Difference, Week 26 – baseline, mean (SD)	0.02 (0.117)	0.01 (0.073)	0.01 (0.008)	0.275
VE/VCO ₂	n=199	n=200		
Difference, Week 26 – baseline, mean (SD)	-1.24 (5.181)	0.04 (6.092)	-1.46 (0.519)	0.005

ANCOVA=analysis of covariance; ITT=intent-to-treat; LS=least squares; SD=standard deviation; SE=standard error; VE/VCO₂=ventilatory equivalents of carbon dioxide; VO₂=minute oxygen consumption

a P-value was assessed using ANCOVA with fixed factors for ventricular morphology (single left versus single right or mixed) and treatment group with a continuous covariate of baseline maximal VO₂.

Source: [Table 14.2.5.1.1](#), [Table 14.2.7.1.1](#), [Table 14.2.8.1.1](#), [Table 14.2.9.1.1](#), [Table 14.2.10.1.1](#), [Table 14.2.11.1.1](#), and [Table 14.2.12.1.1](#)

Program: [T_14_2_5_1_1.sas](#), [T_14_2_7_1_1.sas](#), [T_14_2_8_1_1.sas](#), [T_14_2_9_1_1.sas](#), [T_14_2_10_1_1.sas](#), [T_14_2_11_1_1.sas](#), and [T_14_2_12_1_1.sas](#)

Results based on LOCF, no imputation (observed cases), and imputation with the mean of non-missing values at Week 26 are presented for each measure at peak exercise as shown below.

Measure at Peak Exercise	LOCF		Observed Cases		Week 26 Mean	
	Change	% Change	Change	% Change	Change	% Change
Minute VO ₂	14.2.5.1.1	14.2.5.2.1	14.2.5.1.2	14.2.5.2.2	14.2.5.1.3	14.2.5.2.3
Respiratory rate	14.2.7.1.1	14.2.7.2.1	14.2.7.1.2	14.2.7.2.2	14.2.7.1.3	14.2.7.2.3
Minute ventilation	14.2.8.1.1	14.2.8.2.1	14.2.8.1.2	14.2.8.2.2	14.2.8.1.3	14.2.8.2.3
Work rate	14.2.9.1.1	14.2.9.2.1	14.2.9.1.2	14.2.9.2.2	14.2.9.1.3	14.2.9.2.3
Heart rate	14.2.10.1.1	14.2.10.2.1	14.2.10.1.2	14.2.10.2.2	14.2.10.1.3	14.2.10.2.3
Respiratory exchange ratio	14.2.11.1.1	14.2.11.2.1	14.2.11.1.2	14.2.11.2.2	14.2.11.1.3	14.2.11.2.3
VE/VCO ₂	14.2.12.1.1	14.2.12.2.1	14.2.12.1.2	14.2.12.2.2	14.2.12.1.3	14.2.12.2.3

LOCF=last observation carried forward; VE/VCO₂=ventilatory equivalents of carbon dioxide; VO₂=minute oxygen consumption

11.4.1.4.3 Other Secondary Efficacy Endpoints

A decrease in MPI (improvement in function) from baseline to Week 26 was observed in the udenafil group (-0.02) as compared to an increase in the placebo group (0.01). The least squares mean treatment difference for change in MPI from baseline to Week 26 was -0.03 (p=0.024). Change in MPI from baseline to Week 26 is summarized in [Table 19](#).

Treatment group differences for the remaining ECHO endpoints did not achieve p≤0.05 ([Table 14.2.15.1](#), [Table 14.2.15.2](#), [Table 14.2.15.3](#), [Table 14.2.15.4](#), [Table 14.2.15.5](#), [Table 14.2.15.6](#), [Table 14.2.15.7](#), [Table 14.2.15.8](#), [Table 14.2.15.9](#), [Table 14.2.15.10](#), and [Table 14.2.15.11](#)). Results for individual subjects are presented in [Listing 16.2.6.2.1](#), [Listing 16.2.6.2.2.1](#), and [Listing 16.2.6.2.2.2](#).

Table 19: Change in Myocardial Performance Index Between Week 26 and Baseline Visits (ITT Population)

	Udenafil (N=200)	Placebo (N=200)	Difference LS Mean (SE)	p-value
Baseline	n=150	n=155		
Mean (SD)	0.45 (0.172)	0.45 (0.154)	-0.00 (0.018)	0.925 ^a
Week 26	n=146	n=147		
Mean (SD)	0.42 (0.147)	0.46 (0.177)	-0.04 (0.019)	0.022 ^a
Difference, Week 26 – baseline	n=122	n=127		
Mean (SD)	-0.02 (0.112)	0.01 (0.132)	-0.03 (0.014)	0.024 ^b
Median	-0.01	0.01		

ANCOVA=analysis of covariance; ANOVA=analysis of variance; ITT=intent-to-treat; LS=least squares; SD=standard deviation; SE=standard error

a P-value was assessed using ANOVA with fixed factors for ventricular morphology (single left versus single right or mixed) and treatment group.

b P-value was assessed using ANCOVA with fixed factors for ventricular morphology (single left versus single right or mixed) and treatment group with a continuous covariate of baseline maximal minute oxygen consumption.

Note: No imputation was performed.

Source: [Table 14.2.15](#)

Program: [T_14_2_15.sas](#)

The increase in log-transformed reactive hyperemia index from baseline to Week 26 was larger in the udenafil group (0.06) than in the placebo group (0.04). The least squares mean treatment difference for change in log-transformed reactive hyperemia index from baseline to Week 26 was 0.02 (p=0.410).

The increase in log-transformed BNP from baseline to Week 26 was larger in the udenafil group (0.08 pg/mL) than in the placebo group (0.03 pg/mL). The least squares mean treatment difference for change in log-transformed BNP from baseline to Week 26 was 0.13 pg/mL (p=0.169).

The change in log-transformed reactive hyperemia index and BNP from baseline to Week 26 is summarized in [Table 20](#). Results for individual subjects are presented in [Listing 16.2.6.2.3](#) for BNP and in [Listing 16.2.6.2.4](#) for log-transformed reactive hyperemia index.

Table 20: Change in Endothelial Function and Brain Natriuretic Peptide Between Week 26 and Baseline Visits (ITT Population)

Endpoint	Udenafil (N=200)	Placebo (N=200)	Difference LS Mean (SE)	p-value ^a
Log-transformed reactive hyperemia index	n=175	n=184		
Difference, Week 26 – baseline, mean (SD)	0.06 (0.301)	0.04 (0.364)	0.02 (0.029)	0.410
Log-transformed brain natriuretic peptide (pg/mL)	n=187	n=191		
Difference, Week 26 – baseline, mean (SD)	0.08 (0.905)	0.03 (1.137)	0.13 (0.094)	0.169

ANCOVA=analysis of covariance; ITT=intent-to-treat; LS=least squares; SD=standard deviation; SE=standard error
a P-value was assessed using ANCOVA with fixed factors for ventricular morphology (single left versus single right or mixed) and treatment group with a continuous covariate of baseline maximal minute oxygen consumption.

Note: Brain natriuretic peptide values reported by the laboratory as <2.0 were imputed as 1.0.

Source: [Table 14.2.16](#) and [Table 14.2.17](#)

Program: [T_14_2_16.sas](#) and [T_14_2_17.sas](#)

Change in PedsQL child-reported and parent-reported scale scores from baseline to Week 26 were generally small; no treatment group difference achieved $p \leq 0.05$ ([Table 21](#)). Results for individual subjects are presented in [Listing 16.2.6.3.1](#), [Listing 16.2.6.3.2](#), [Listing 16.2.6.3.3](#), and [Listing 16.2.6.3.4](#).

Table 21: Difference in Pediatric Quality of Life Inventory Endpoints Between Week 26 and Baseline Visits (ITT Population)

	Udenafil (N=200)	Placebo (N=200)	LS Mean Difference (SE)	p-value ^a
PedsQL Generic Core Scales				
Physical functioning (child-reported)	n=186	n=193		
Difference, Week 26 – baseline, mean (SD)	2.08 (12.006)	1.53 (11.823)	0.44 (1.100)	0.691
Physical functioning (parent-reported)	n=181	n=181		
Difference, Week 26 – baseline, mean (SD)	2.74 (18.011)	1.94 (15.328)	0.03 (1.544)	0.985
Psychosocial health summary score (child-reported)	n=185	n=193		
Difference, Week 26 – baseline, mean (SD)	2.84 (11.356)	1.74 (10.700)	1.14 (1.039)	0.273
Psychosocial health summary score (parent-reported)	n=181	n=181		
Difference, Week 26 – baseline, mean (SD)	2.64 (13.546)	2.15 (13.737)	-0.06 (1.327)	0.966
PedsQL Cardiac Module Scales				
Treatment II (child-reported)	n=164	n=173		
Difference, Week 26 – baseline, mean (SD)	0.24 (11.655)	-0.09 (9.046)	-0.38 (1.011)	0.706
Perceived physical appearance	n=184	n=192		
Difference, Week 26 – baseline, mean (SD)	2.45 (20.819)	0.78 (17.396)	1.50 (1.707)	0.382
Treatment anxiety	n=184	n=192		
Difference, Week 26 – baseline, mean (SD)	3.37 (19.258)	1.66 (16.477)	1.91 (1.611)	0.236
Cognitive problems	n=183	n=192		
Difference, Week 26 – baseline, mean (SD)	2.19 (16.826)	3.05 (17.027)	-0.99 (1.622)	0.543
Communication problems	n=183	n=192		
Difference, Week 26 – baseline, mean (SD)	1.82 (20.406)	4.36 (17.954)	-1.66 (1.780)	0.352

ANCOVA=analysis of covariance; ITT=intent-to-treat; LS=least squares; PedsQL=Pediatric Quality of Life

Inventory; SD=standard deviation; SE=standard error

a P-value was assessed using ANCOVA with fixed factors for ventricular morphology (single left versus single right or mixed) and treatment group with a continuous covariate of baseline value.

Source: [Table 14.2.18.1](#), [Table 14.2.18.2](#), [Table 14.2.18.3](#), [Table 14.2.18.4](#), [Table 14.2.18.5](#), [Table 14.2.18.6](#), [Table 14.2.18.7](#), [Table 14.2.18.8](#), and [Table 14.2.18.9](#)

Program: [14_2_18.sas](#)

Mean treatment group differences in change from baseline to Week 26 in PCQLI child-reported and parent-reported total scores were generally small; no treatment group

difference achieved $p \leq 0.05$ ([Table 22](#)). Results for individual subjects are presented in [Listing 16.2.6.4.1](#) and [Listing 16.2.6.4.2](#).

Table 22: Difference in Pediatric Cardiac Quality of Life Inventory Endpoints Between Week 26 and Baseline Visits (ITT Population)

PCQLI Score	Udenafil (N=200)	Placebo (N=200)	LS Mean Difference (SE)	p-value ^a
Total score for 8-12 (child-reported)	n=16	n=12		
Difference, Week 26 – baseline, mean (SD)	3.26 (12.287)	-2.37 (16.368)	3.59 (5.684)	0.533
Total score for 8-12 (parent-reported)	n=17	n=11		
Difference, Week 26 – baseline, mean (SD)	-0.91 (13.399)	-4.44 (6.389)	1.84 (4.057)	0.654
Total score for 13-18 (child-reported)	n=158	n=170		
Difference, Week 26 – baseline, mean (SD)	-0.08 (11.032)	0.09 (9.626)	-0.05 (1.069)	0.963
Total score for 13-18 (parent-reported)	n=152	n=162		
Difference, Week 26 – baseline, mean (SD)	0.36 (11.722)	-1.60 (11.179)	1.36 (1.171)	0.246

ANCOVA=analysis of covariance; ITT=intent-to-treat; LS=least squares; PCQLI=Pediatric Cardiac Quality of Life Inventory; SD=standard deviation; SE=standard error

a P-value was assessed using ANCOVA with fixed factors for ventricular morphology (single left versus single right or mixed) and treatment group with a continuous covariate of baseline value.

Source: [Table 14.2.19.1](#), [Table 14.2.19.2](#), [Table 14.2.19.3](#), and [Table 14.2.19.4](#)

Program: [14_2_19.sas](#)

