After completion of the Phase 1/2 study, Mezzion Pharma Co. Ltd continued its partnership with the PHN to create and execute the FUEL study. This 400-patient, double-blind, placebo-controlled trial is the largest medication trial ever undertaken for those with any form of congenital heart disease and was conducted to determine the safety and efficacy of daily oral therapy with udenafil in adolescents with single ventricle heart disease who had undergone Fontan palliation. The primary aim was to determine the effect of udenafil on exercise performance over a 26-week treatment period. Safety was evaluated throughout the 26-week period and for up to an additional 3 months. Mezzion Pharma Co. Ltd and the PHN are also conducting an open-label extension trial to continue to evaluate the tolerability and safety of udenafil over an additional 3-year time period.

8 Study Objectives

The primary objective of the study was to evaluate the effect of 26 weeks of treatment with udenafil (87.5 mg, BID) on exercise capacity in adolescents with Fontan physiology.

The secondary objectives of this study of adolescents with Fontan physiology were to:

- Determine the effect of 26 weeks of treatment with udenafil on echocardiographic indices of systolic and diastolic ventricular performance.
- Determine the effect of 26 weeks of treatment with udenafil on endothelial function.
- Evaluate the effect of 26 weeks of treatment with udenafil on serum brain natriuretic peptide (BNP) level, a biomarker of heart failure.
- Evaluate the safety of udenafil when given over a 26-week time period.
- Determine if 26 weeks' treatment with udenafil alters functional health status.
- Establish a collection of genetic material to identify genetic determinants of exercise capacity and response to udenafil and for unspecified future studies.
- Determine the prevalence and severity of complications, including protein-losing enteropathy, plastic bronchitis, hospitalizations, cardiac transplantation and death in adolescents who received udenafil.
- Explore the impact of udenafil on atrial and ventricular premature beats and arrhythmia burden.

9 Investigational Plan

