Studies have demonstrated a strong correlation between endothelial function and exercise capacity, including recent data utilizing EndoPAT in the assessment of endothelial function ([Goldstein 2011](#); [Goldstein 2016](#)). Based on the known effect of PDE-5 inhibitors and the known endothelial dysfunction in the Fontan population ([Mahle 2003](#); [Inai 2004](#); [Jin 2007](#); [Binotto 2008](#)), a measure of endothelial function is a useful candidate marker for a potential pharmacodynamic effect. The Framingham-modified RHI and raw RHI measures served as secondary outcome measures of vascular function.

Serum BNP is a useful biomarker in patients with heart failure from a variety of causes. A study of BNP levels in 510 patients after the Fontan procedure (median age 11.4 years) performed through the PHN revealed mean BNP levels of 25 ± 48 pg/mL ([Atz 2011](#)). Higher BNP was associated with several markers of suboptimal outcomes albeit with weak associations but may be a predictor of Fontan failure. In the pilot study by Goldberg, those with a serum BNP level >100 pg/mL had a more robust response to sildenafil ([Goldberg 2011](#)). Thus, BNP may be helpful in measuring a response to medical intervention.

The quality of life and functional status questionnaires have been widely used in multiple studies. The safety and PK measurements utilized were standard, widely used, and generally recognized as reliable, accurate, and relevant to the study population and study design.

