9.7 Statistical Methods Planned in the Protocol and Determination of Sample Size

9.7.1 Statistical and Analytical Plans

The statistical methods described below are summarized from the final Statistical Analysis Plan (SAP), dated 23 June 2016. Changes from the planned analyses in the protocol that were specified in the final SAP are described in [Section 9.8.2](#).

Formal hypothesis testing was performed only for the primary efficacy endpoint. All statistical tests were at the 0.05 alpha level, 2-tailed, unless stated otherwise. Descriptive statistics for categorical endpoints included the number and percent of subjects in each treatment group and category. Quantitative endpoints were summarized for each treatment group with the mean, median, standard deviation, minimum value, and maximum value. Individual subject data were presented in data listings that included normal reference ranges when appropriate.

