impact of alterations in PVR on exercise capacity for those with other forms of heart disease. Although udenafil may have some effect on maximal VO₂, this effect is blunted by the physiologic ceiling of CVP. The expanded understanding of Fontan physiology in recent years has taught that the assumptions informing the selection of maximal VO₂ as the primary endpoint were inaccurate, and that VO₂ at VAT is a more useful endpoint for this unique cohort of patients.

Overall Efficacy Conclusions

In summary, treatment with udenafil for 26 weeks resulted in improvements in exercise capacity, as well as an improvement in the performance of the single ventricle. Although the primary endpoint did not reach statistical significance, new knowledge of the limits of the Fontan circulation explains why this endpoint is an imperfect choice for this circulation. Even with the limitations associated with maximal VO₂, this endpoint showed a clear trend toward improvement that, coupled with the improvement at the anaerobic threshold, speaks to the efficacy of udenafil to improve exercise capacity in this population. Based on the superior exercise capacity and ventricular performance for udenafil as compared to placebo at Week 26, this study achieved its primary clinical objective for a population with no pharmacotherapeutic options.

12 Safety Evaluation

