6.4.2 Secondary Efficacy Endpoints

Secondary efficacy endpoints include change from baseline to Visit 4 (Week 26) in:

- Exercise capacity
 - Minute oxygen consumption at the ventilator anaerobic threshold (VAT)
 - Ventilatory equivalents of carbon dioxide (VE/VCO₂) at VAT
 - Respiratory rate and minute ventilation at peak exercise
 - Maximal work rate
 - Work rate at the VAT
- Ventricular performance
 - Myocardial performance index (MPI) determined by velocities obtained from blood pool Doppler assessment of the inflow and outflow tract of the dominant ventricle. It is the primary performance endpoint of the echocardiogram.
 - Ventricular cavity size, eccentricity, and mass (based on echocardiogram)
 - Systolic function estimate using mean dP/dt during isovolumetric contraction (dP/dt_{ic}) and peak systolic annular velocity (S') on tissue Doppler
 - Qualitative and quantitative estimate of atrioventricular valve insufficiency
- Endothelial function: log-transformed reactive hyperemia index (lnRHI), as measured by pulse amplitude tonometry (PAT) testing using the EndoPAT® device
- Natural logarithm transformation of BNP
- Functional health status as measured by the full scale PedsQL
 - Physical functioning score

CONFIDENTIAL

- Psychosocial functioning score
- Cardiac-specific quality-of-life score
- Pediatric Cardiac Quality of Life Inventory (PCQLI) score

Each secondary efficacy endpoint will be summarized descriptively by treatment group.

Treatment group differences for endpoints associated with the PedsQL and PCQLI will be assessed with Friedman's test using ventricular morphology (single left versus single right or mixed) as the stratification factor. The treatment group difference for the qualitative estimate of atrioventricular valve insufficiency will be assessed with a Cochran-Mantel-Haenszel test using ventricular morphology (single left versus single right or mixed) as the stratification factor.

The remaining secondary efficacy endpoints will be analyzed with the ANCOVA model with fixed factors for ventricular morphology (single left versus single right or mixed) and treatment group with a covariate for the baseline value.

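### Log-scale BNP changes are printed in pg/mL: the 0.13 is a udenafil/placebo ratio of about 1.14 (95% CI 0.95 to 1.37), and the text does not say that a larger increase is unfavourable

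*Protocol*

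**What the plan says.** SAP section 6.4.2 lists the endpoint as "Natural logarithm transformation of BNP", and section 9.7.1.4.2 of the protocol document does the same. The planned analysis is an ANCOVA with ventricular morphology, treatment group and the baseline value of the endpoint.

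Section 11.4.1.4.3 gives the group results: "The increase in log-transformed BNP from baseline to Week 26 was larger in the udenafil group (0.08 pg/mL) than in the placebo group (0.03 pg/mL"). Next comes the comparison: "The least squares mean treatment difference for change in log-transformed BNP from baseline to Week 26 was 0.13 pg/mL (p=0.169"). Table 20 repeats the figures with SDs, a standard error of 0.094 and n=187 and n=191. It labels the log-transformed row with pg/mL and names baseline maximal VO2 as the covariate. A note adds that values reported as below 2.0 were set to 1.0.

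On what BNP means, section 8 names as a secondary objective the effect on "serum brain natriuretic peptide (BNP) level, a biomarker of heart failure". Section 9.5.2 says: "Higher BNP was associated with several markers of suboptimal outcomes albeit with weak associations".

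Section 11.4.1.4.3 does give a clinical reading for MPI: "A decrease in MPI (improvement in function) from baseline to Week 26 was observed in the udenafil group (-0.02"). It gives none for BNP.

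**The concern.** A difference between two natural logs is the log of a ratio. It has no concentration unit, and 0.13 is not 0.13 pg/mL. The same error affects both group changes (0.08 and 0.03) and the row label in Table 20. The report handles other log-scale results correctly: the log reactive hyperemia index in the same section and the log VO2 changes in section 11.4.1.2 are printed without a concentration unit.

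The reported effect for a stated secondary objective therefore cannot be read as printed. A reader who trusts the unit sees an absolute change. A reader who trusts the words log-transformed has to find the base elsewhere, because neither the results sentence nor Table 20 gives it. No ratio and no confidence interval is printed.

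The second gap is interpretation. The direction of the difference is given, but the results text does not tell the reader that a larger increase in this marker is the unfavourable direction.

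**Working it through.** **Inputs.** Adjusted difference 0.13, SE 0.094, printed p=0.169; raw mean changes (SD) 0.08 (0.905) with n=187 on udenafil and 0.03 (1.137) with n=191 on placebo (section 11.4.1.4.3 and Table 20). Natural log (SAP 6.4.2). Section 9.7.1: "All statistical tests were at the 0.05 alpha level, 2-tailed, unless stated otherwise".

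**1. Reproduce the printed p-value.**
- t = 0.13 / 0.094 = 1.383.
- df = 187 + 191 − 4 = 374 (intercept, morphology, treatment, one covariate).
- Two-sided p = 0.167. Rounding of the printed difference (0.125 to 0.135) and SE (0.0935 to 0.0945) allows 0.150 to 0.187, so 0.169 is consistent. The estimate, SE and p-value agree with each other; the fault is the unit.

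**2. Back-transform the adjusted difference.**
- Ratio = exp(0.13) = 1.139.
- 95% limits on the log scale: 0.13 ± 1.96 × 0.094 = −0.054 to 0.314.
- As ratios: exp(−0.054) = 0.947 and exp(0.314) = 1.369. Using the t quantile gives 0.947 to 1.370.
- Over the rounding range the ratio is 1.133 to 1.145, the lower limit 0.941 to 0.952 and the upper limit 1.362 to 1.378.
- In words: the relative increase is estimated as about 14% larger on udenafil, with an interval from 5% smaller to 37% larger.
- The base matters. Read as a base-10 log, 0.13 would give 10^0.13 = 1.35.

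**3. Unadjusted comparison from the same table row.**
- Difference = 0.08 − 0.03 = 0.05.
- SE = √(0.905²/187 + 1.137²/191) = 0.106.
- Ratio = exp(0.05) = 1.051; 95% CI = exp(0.05 ± 1.96 × 0.1056) = 0.855 to 1.293; p = 0.64.
- Rounding of the two means allows a difference of 0.04 to 0.06, a ratio of 1.04 to 1.06.

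**4. Which model produced 0.13?** Adjustment moves the difference from 0.05 to 0.13, so the covariate matters. The passages disagree:
- Table 20 footnote: baseline maximal VO2.
- SAP 6.4.2 and section 9.7.1.4.2: the baseline value of the endpoint.
- Section 11.4.2.1: the relevant baseline value.

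The footnotes to Tables 15, 17, 18 and 19 also name baseline maximal VO2, while Tables 21 and 22 name the baseline value. The Table 20 footnote may therefore be carried-over text, but the documents do not settle it.

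**The case against.** The strongest reply is that this is a label error on one non-significant secondary endpoint. The text and Table 20 both call the values log-transformed, the estimate, SE and p-value agree, and no test or decision depends on the unit. Log-scale display is also the report's habit: section 9.8.2.3 says geometric mean ratios were calculated for VO2, yet Tables 14 and 16 print log differences, including favourable ones. All of this stands. It limits the point to a reporting correction, but it does not make pg/mL right.

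Four stronger readings are tempting, and the documents do not support them.

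- *The direction is concealed.* It is not. The sentence before the treatment difference says that the increase was larger on udenafil. Only the evaluation is missing, and the non-significant log reactive hyperemia index has no evaluative label either.
- *Udenafil raises BNP by 14%.* The interval includes 1, the raw means give about 5%, the covariate is unconfirmed, and section 11.4.2.5 says that secondary endpoints were neither formally tested nor adjusted for multiplicity.
- *BNP undercuts the conclusion in section 11.4.7.* That section says: "Based on the superior exercise capacity and ventricular performance for udenafil as compared to placebo at Week 26". BNP is absent there and from section 13. So are the log reactive hyperemia index, the quality-of-life scores and the favourable peak VE/VCO2 result (p=0.005), so selective omission is not shown. SAP 6.4.2 makes MPI the primary echocardiographic performance endpoint and lists BNP separately. A non-significant BNP difference does not contradict the MPI result.
- *The effect can be scaled against the BNP mean of 25 pg/mL in section 9.5.2.* That is an arithmetic mean with an SD of 48 from another cohort. It says nothing reliable about levels in this trial, which the report does not give.

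**Conclusion.** The point holds as a reporting error with one interpretive gap. The 0.08, 0.03 and 0.13 in section 11.4.1.4.3, and the row label in Table 20, carry a unit that log-scale values cannot have. Correctly expressed, the reported treatment effect is a udenafil/placebo ratio of geometric mean change of about 1.14 (95% CI 0.95 to 1.37, p=0.169).

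This rests on the natural log stated in SAP 6.4.2 and on the printed estimate and standard error. The unit error stands whichever covariate was used; the figure 1.14 does not, and it should be treated as provisional until the model is confirmed. It is also conditional on setting values below 2.0 to 1.0, which affects the log scale.

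The result is imprecise and compatible with no difference. It is neither evidence of harm nor evidence of benefit.

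**What to change.** 1. In section 11.4.1.4.3 and Table 20, delete pg/mL from every log-scale value and label, and state that the log is natural.
2. Confirm which covariate produced 0.13. If it was the endpoint's own baseline, correct the Table 20 footnote. If it was baseline maximal VO2, rerun the model as planned in SAP 6.4.2, or record the departure among the changes to planned analyses in section 9.8.2.
3. Then report the udenafil/placebo ratio of geometric mean change with its 95% CI: 1.14 (0.95 to 1.37) if the printed estimate is confirmed. Showing the unadjusted ratio of about 1.05 beside it would make the effect of adjustment visible.
4. State that a ratio above 1 is the unfavourable direction, that the result is not statistically significant and that it is not multiplicity-adjusted. Speak of a larger increase rather than a higher level, because Table 20 reports only changes.
5. Optionally, mention BNP with the other null secondary results in sections 11.4.7 and 13.

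The cost is one model check, a back-transformation and a few sentences. If the covariate was not the planned one, it also includes one rerun of an existing analysis. The primary result is unaffected.
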